Administration of study drug will occur at Week 0, 12, 24 and 36, with an additional dose of rizankizumab made available at the Week 4 visit for those subjects that have not achieved a protocol defined response (defined as an improvement in tender and swollen joint count of \geq 20% compared with the baseline in Study 1311.5), provided the investigator believes this may be beneficial to the subject. Subjects who have not attained a protocol defined response at 2 consecutive visits at Week 12 visit or thereafter, will be discontinued from the OLE study. Other criteria leading to discontinuation of individual subjects in this trial are described in Section [5.4.1](#).

A \pm 4-day window is permitted around scheduled study visits after enrollment. If any visit has to be rescheduled, subsequent visits should follow the original visit date schedule.

Follow-Up Period

Subjects will have follow-up visits at Week 48 and 52 and a Follow-up Phone call 20 weeks after the last dose of study drug. All Follow-up Visit procedures are noted in [Appendix C](#). Subjects who discontinue study drug treatment early will need to attend an early End of Treatment (EOT) visit ideally within 2 weeks after the decision and preferably prior to the administration of any new therapies. An End of Study (EOS) visit 16 weeks after the last dose of study drug and a Follow-up Phone Call 20 weeks after the last dose of study drug is required to determine the status of any ongoing AEs/SAEs or the occurrence of any new AEs/SAEs (see [Appendix C](#) and Section [5.4.1](#)).

A schematic of the study design is shown below in [Figure 2](#).

Figure 2. Study M16-244 Study Design

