5.4 Removal of Subjects from Therapy or Assessment

5.4.1 Discontinuation of Individual Subjects

A subject may withdraw from the study at any time. The Investigator may discontinue any subject's participation for any reason, including an adverse event, safety concerns or failure to comply with this protocol.

Subjects will be withdrawn from the study drug and prematurely discontinued if any of the following occur:

- A subject does not attain a protocol defined response (defined as an improvement in tender and swollen joint count of $\geq 20\%$ compared with the baseline in Study 1311.5) at 2 consecutive visits at Week 12 visit, or thereafter.
- A subject experiences a moderate/grade 2 or above (Rheumatology Common Toxicity Criteria v 2.0) non-serious AE of a systemic hypersensitivity reaction, for which there is no clear alternative explanation.
- A subject experiences a moderate/grade 2 adverse event of vasculitis (Rheumatology Common Toxicity Criteria v 2.0) for which there is no clear alternative explanation.
- Subject experiences severe, grade 3 or greater, or life threatening injection site reaction (ISR) (as defined by the Rheumatology Common Toxicity Criteria v 2.0) which includes prolonged induration, superficial ulceration and includes thrombosis or major ulceration or necrosis requiring surgery.
- A subject has a confirmed platelet count $< 50,000$ cells/mm³ (Rheumatology Common Toxicity Criteria v 2.0).
- Clinically significant confirmed abnormal laboratory results or adverse events, which rule out continuation of the study drug, as determined by the Investigator and the AbbVie study designated physician.
- The Investigator believes it is in the best interest of the subject.
- The subject requests withdrawal from the study, and is no longer willing to participate in study procedures or receive contact from the site.
- Inclusion and exclusion criteria violation was noted after the subject started study drug, when continuation of the study drug would place the subject at risk as determined by the AbbVie study designated physician.
- Introduction of prohibited medications or dosages when continuation of the study drug would place the subject at risk as determined by the AbbVie study designated physician.
- The subject becomes pregnant while on study drug.

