- Subject is significantly non-compliant with study procedures which would put the subject at risk for continued participation in the trial in consultation with the AbbVie study designated physician.

If, during the course of study drug administration, the subject prematurely discontinues study participation, the procedures outlined for the early EOT visit must be completed, ideally within 2 weeks of the decision and preferably prior to the initiation of another therapy. However, these procedures should not interfere with the initiation of any new treatments or therapeutic modalities that the Investigator feels are necessary to treat the subject's condition. For subjects that prematurely discontinue, study drug will not be given at the early EOT visit and subjects should attend their EOS Visit 16 weeks after last study drug dose and complete a Follow-up Phone Call 20 weeks after the last dose of study drug to determine the status of any ongoing AEs/SAEs or the occurrence of any new AEs/SAEs (see [Appendix C](#)).

Subjects who prematurely discontinue from study drug will not be required to collect x-rays at a designated time point, unless they received a dose within the 16 weeks prior to the scheduled time point.

All attempts must be made to determine the primary reason for premature discontinuation. The information will be recorded on the appropriate eCRF page.

For subjects that are considered lost to follow-up, reasonable attempts must be made to obtain information on the final status of the subject. At a minimum, two phone calls must be made and one certified letter must be sent and documented in the subject's source documentation.

Subjects who discontinue the study prematurely will not be replaced.

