6.1.1 Definitions

6.1.1.1 Adverse Event

An adverse event (AE) is defined as any untoward medical occurrence in a patient or clinical investigation subject administered a pharmaceutical product and which does not necessarily have a causal relationship with this treatment. An adverse event can therefore be any unfavorable and unintended sign (including an abnormal laboratory finding), symptom, or disease temporally associated with the use of a medicinal (investigational) product, whether or not the event is considered causally related to the use of the product.

Such an event can result from use of the drug as stipulated in protocol or labeling, as well as from accidental or intentional overdose, drug abuse, or drug withdrawal. Any worsening of a pre-existing condition or illness is considered an adverse event.

Worsening in severity of a reported adverse event should be reported as a new adverse event. Laboratory abnormalities and changes in vital signs are considered to be adverse events only if they result in discontinuation from the study, necessitate therapeutic medical intervention, and/or if the investigator considers them to be adverse events.

An elective surgery/procedure scheduled to occur during a study will not be considered an adverse event if the surgery/procedure is being performed for a pre-existing condition and the surgery/procedure has been pre-planned prior to study entry. However, if the pre-existing condition deteriorates unexpectedly during the study (e.g., surgery performed earlier than planned), then the deterioration of the condition for which the elective surgery/procedure is being done will be considered an adverse event.

Prior to use, every attempt should be made to contact the AbbVie Study Designated Physician for direction on re-introduction of study drug therapy after prohibited medication administration.

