## 5.0 Analysis Sets

### 5.1 Definition for Analysis Sets

#### Safety Analysis Set

The Safety Analysis Set consists of all subjects who have received at least one dose of study medication in Study M16-244. All efficacy and safety analyses will be based on the Safety Analysis Set.

All efficacy and safety analyses will be summarized for "All ABBV-066 150 mg q12wks with optional wk4 dose" group, which includes all subjects who received at least one dose of ABBV-066 150 mg every 12 weeks in Study M16-244 (with an optional additional dose at Week 4 for subjects with < 20% improvement in tender joint count (TJC) or swollen joint count (SJC)), regardless of what treatment group they were randomized to in Study 1311.5.

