## **6.4                   Definition of Analysis Windows**

All time points and corresponding time windows are defined based on Rx Days.

For efficacy analyses, laboratory parameters, and vital sign variables, analysis windows are constructed using the following algorithm:

- Determine the nominal Rx day for each visit (e.g., Week 4 [4 weeks after Baseline visit] equals Rx Day 29).
- In order to include all post baseline data, the first post-baseline interval starts on the first day after the first dose of study drug (Rx Day 2).

---

- Determine the window around a specific nominal Rx day by adding or subtracting half of the interval between adjacent visits (e.g., days between Week 2 and Week 4 is 14). The threshold between adjacent visits is determined by splitting the interval evenly between the visits. If the resulting split is between Rx days, then the threshold is determined as the midpoint between the adjacent visits. If the resulting split is on a Rx day, then the threshold is determined as being between that Rx day and the Rx day prior to it (e.g., the split between Week 2 and Week 4 would be between Rx Days 22 and 23).
- If more than one assessment is included in a time window the assessment closest to the nominal day will be used. If there are two observations equidistant to the nominal day, the one after the nominal day will be used in analyses. If more than one assessment is included on the same day, then the worst assessment on that day will be used in analyses. For laboratory values, if there are multiple measurements on the same day, average value will be used.

The protocol specified visits and corresponding time windows used in the various efficacy analyses, laboratory parameters, and vital sign variables, are presented in the following tables.

**Table 1. Analysis Windows for Efficacy Variables (PtGA, Patient's Assessment of PsA Pain Intensity, HAQ-DI, SF-36v2, TJC68, SJC66, PASI, BSA, sPGA, PhGA, hsCRP for DAS)**

Protocol Specified Visit Week	Lower Bound	Target Day	Upper Bound
0	1	1	1
4	2	29	57
12	58	85	127
24	128	169	211
36	212	253	295
48	296	337	351
52	352	365	378

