## 6.5 Missing Data Handling

All data will be summarized as observed, and thus a subject who does not have an evaluation on a scheduled visit will be excluded from the summary for that visit.

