### 10.3 Secondary Efficacy Analyses

The following secondary endpoints will be summarized:

- ACR 20 response at all measured time points in Study M16-244
- Change in mTSS at Week 24 (Study 1311.5), Week 24 (Study M16-244), and Week 48 as compared to baseline in Study 1311.5
- Change in HAQ-DI at all measured time points in Study M16-244 compared to baseline in Study 1311.5
- Change SF-36 at all measured time points in Study M16-244 compared to baseline in Study 1311.5

For the change from baseline in continuous endpoints, the number of observations, mean, standard deviation, median, minimum, Q1, Q3 and maximum will be summarized. Point estimates and 95% CIs of mean change from baseline will be provided.

For the summary of binary endpoints by visit, point estimate and 95% CI will be calculated and presented.

The primary analysis for the above secondary efficacy endpoints will be performed based on the Safety Analysis Set with observed cases.

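### Efficacy is summarised as observed with no rule for data collected after prohibited or replacement PsA therapy starts, so some other-drug values can enter the risankizumab visit summaries

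*SAP*

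**What the plan says.** **Analysis rules.** SAP 5.1: "All efficacy and safety analyses will be based on the Safety Analysis Set", meaning everyone dosed at least once in the extension, pooled into one risankizumab group. SAP 6.5: "All data will be summarized as observed, and thus a subject who does not have an evaluation on a scheduled visit will be excluded". SAP 10.3 repeats this for ACR20, mTSS, HAQ-DI and SF-36: "The primary analysis for the above secondary efficacy endpoints will be performed based on the Safety Analysis Set with observed cases". SAP Table 8 applies observed cases to every other efficacy endpoint. SAP 6.4: "All time points and corresponding time windows are defined based on Rx Days". Within a window the record closest to the target day is used and, if two are equally close, the one after the target day. For ACR, SAP 10.7.1 takes the closest non-missing composite.

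**Prohibited therapy.** Protocol 5.2.3.3 bars other PsA biologics, JAK inhibitors, apremilast, leflunomide and injected corticosteroids, among others, for the whole study. The matching withdrawal criterion in protocol 5.4.1 is conditional: "Introduction of prohibited medications or dosages when continuation of the study drug would place the subject at risk". Protocol 6.1.1.1 tells sites to seek "direction on re-introduction of study drug therapy after prohibited medication administration".

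**Replacement therapy after an early stop.** Protocol 5.4.1 asks for an early end-of-treatment (EOT) visit, preferably before new therapy, but "these procedures should not interfere with the initiation of any new treatments or therapeutic modalities that the Investigator feels are necessary". Protocol 5.1 then requires "An End of Study (EOS) visit 16 weeks after the last dose of study drug". Appendix C schedules joint counts, PASI, HAQ-DI and hsCRP at that end-of-study (EOS) visit.

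**Tracking.** SAP 7.4 counts subjects who received prohibited treatment and removes no data. The SAP 7.3 list of summarised concomitant medications has no line for biologic DMARDs.

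**The concern.** The secondary objective is the efficacy of risankizumab, and the study has one arm. If a subject improves on another agent and that value is tabulated under a scheduled visit, no comparator arm exposes it, and the table does not show which drug the subject was taking. This differs from bias through absent subjects: here the data are present but may reflect another therapy.

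Elsewhere the documents do tie data to dosing. SAP 6.2 and 11.2.1 use a 140-day limit after the last dose for safety. Protocol 5.4.1 waives x-rays after early discontinuation unless a dose was given in the preceding 16 weeks. The clinical efficacy endpoints have no equivalent limit, either at the last dose or at the start of other therapy. At stake are the visit-wise response rates with their exact 95% intervals, ACR20 above all, and the mean changes.

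**Working it through.** The documents contain no power or effect calculation to reproduce. What can be checked is the window table, where the EOS record lands, and how the rate moves.

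**1. SAP Table 1 cut-points.** Midpoints of adjacent target days: (29+85)/2 = 57; (85+169)/2 = 127; (169+253)/2 = 211; (253+337)/2 = 295; (337+365)/2 = 351. All match the stated upper bounds.

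**2. Where EOS falls.** EOS day = last-dose day + 16 × 7 = last-dose day + 112.

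| Last dose | EOS day | Table 1 window | Days from target |
|---|---|---|---|
| Week 0, Day 1 | 113 | Week 12 (58-127) | 113 − 85 = 28 |
| Week 4, Day 29 | 141 | Week 24 (128-211) | 169 − 141 = 28 |
| Week 12, Day 85 | 197 | Week 24 (128-211) | 197 − 169 = 28 |
| Week 24, Day 169 | 281 | Week 36 (212-295) | 281 − 253 = 28 |

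The ±4-day visit allowance changes none of these windows.

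**3. When the EOS record is actually used.**

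- *Stopped at a scheduled visit: usually not used.* Last dose Day 1, stopped at Week 12: Day 85 (distance 0) beats Day 113. Last dose Day 85, stopped at Week 24: Day 169 beats Day 197. Last dose Day 169, stopped at Week 36: Day 253 beats Day 281.
- *Stopped between visits: often used.* Last dose Day 85 and early EOT by Day 127: the EOT record lies in the Week 12 window, so Day 197 is the only Week 24 record. An early EOT on Days 128-140 is 41 to 29 days from Day 169 and loses to Day 197 at 28 days. On Day 141 the two tie and the later one is taken. From Day 142 the EOT record is used.
- *Stopped at Week 12 after the optional Week 4 dose: used.* The Day 85 record belongs to Week 12, and EOS on Day 141 is the only Week 24 record.
- *ACR with an indeterminate earlier composite: used*, because the rule takes the closest non-missing composite.

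**4. Subjects kept on study after prohibited therapy.** They attend ordinary visits near the target days, so the closest-record rule gives no protection and every later value is used.

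**5. Effect on a response rate.** Let n be the records at a visit, s those taken after a switch, R the responders among the other n − s, and x the responders among the s.

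- Planned: (R + x)/n
- Post-switch set to non-response: R/n. Planned minus this is x/n, which is never negative.
- Post-switch excluded: R/(n − s). The planned rate is a weighted mean of R/(n − s) and x/s, so it can lie on either side.

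Illustration. These inputs are assumptions, not in the documents: n = 180, 60% response without a switch, 40% or 60% response after one, counts rounded.

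| s | R | x | Planned | Non-response | Excluded | Planned minus non-response |
|---|---|---|---|---|---|---|
| 9 (5%) | 103 | 4 or 5 | 59.4 or 60.0% | 57.2% | 60.2% | 2.2 or 2.8 points |
| 18 (10%) | 97 | 7 or 11 | 57.8 or 60.0% | 53.9% | 59.9% | 3.9 or 6.1 points |
| 27 (15%) | 92 | 11 or 16 | 57.2 or 60.0% | 51.1% | 60.1% | 6.1 or 8.9 points |

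Direction against exclusion, at s = 18: if 7 respond, 104/180 = 57.8%, below 59.9%. If all 18 respond, 115/180 = 63.9%, above it. A single post-switch responder adds 1/180 = 0.6 points over the non-response rule.

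**The case against.** Observed cases in all dosed subjects is openly stated and fits a treatment-policy summary. Efficacy is secondary, there is no primary efficacy endpoint and no testing, so neither type I error nor power is affected. Prohibited-treatment deviations are tabulated, and concomitant corticosteroids and non-MTX csDMARDs are summarised. EOS at 112 days lies inside the SAP's own 140-day residual effect period. Completers are likewise assessed 16 weeks after their last dose, at Week 52. Table 1 labels visit weeks and does not claim that subjects are on treatment.

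Most of this stands and limits the point. The issue is therefore other therapy, not elapsed time since the last dose. A treatment-policy reading is defensible, but neither document adopts it, and a deviation count does not show which responders were on another drug.

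Three stronger readings are tempting and unsupported:

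- *Every early stopper supplies a post-switch value.* The closest-record rule usually selects the earlier visit for those stopped at a scheduled visit, including many withdrawn for non-response.
- *The error always runs upward.* That is guaranteed only against a non-response rule.
- *The bias can be put at a definite number of points.* The documents give no rate of stopping, of switching, or of response after a switch.

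**Conclusion.** The gap is real. No rule in either document removes or recodes efficacy data after prohibited or replacement PsA therapy, and both routes for such data are open on the text. Retention on study after prohibited therapy has no protection from window selection. The early-stop route is narrower: mainly stops between visits, a Week 12 stop after the optional Week 4 dose, and indeterminate earlier ACR composites.

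The size is unknown. The 2.2 to 8.9 points rests entirely on the assumed 5-15% of post-switch records and 40-60% response among them. Given how narrow the second route is, the upper end is a generous assumption. The consequence is a description of efficacy whose meaning is unclear. The primary safety objective is untouched. The point merits an SAP change.

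**What to change.** Add to SAP 6.5: from the start date of a prohibited systemic or intra-articular PsA therapy (TNF inhibitor, anti-IL-17, anti-IL-12/23, cell-depleting agent, JAK inhibitor, apremilast, leflunomide, intra-articular or IM/IV corticosteroid), or of any new systemic PsA therapy after the last study dose, binary efficacy endpoints are set to non-response and continuous values are excluded. State whether non-response also applies at later scheduled visits without an evaluation; otherwise a switcher who attends counts against the rate and one who does not simply drops out.

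If as-observed remains the main summary, say that it is regardless of other therapy, and present this analysis beside it for ACR20 and the other secondary endpoints.

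Limit any rule for topical psoriasis treatment to the skin endpoints; otherwise one topical course would force lasting non-response on joint measures. Do not tie a rule to MTX or corticosteroid dose relative to the Study 1311.5 baseline. Protocol 5.2.3.2 requires stability only before extension enrolment (4 weeks for MTX, 2 for corticosteroids), so a subject whose dose rose during Study 1311.5 could enter compliantly and be a non-responder throughout.

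Flag EOS records taken after early discontinuation, list the affected subjects, and add concomitant biologic DMARDs to the SAP 7.3 summary.

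Cost: one SAP paragraph and a programming flag from medication dates that protocol 5.2.3 already requires on the eCRF. Reported response rates may be slightly lower, a few continuous values are lost, and a one-off injection is treated strictly. No clinical rule changes.

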PsA	Psoriatic Arthritis
PsARC	Psoriatic Arthritis Response Criteria
PsO	Psoriasis
PT	Preferred Term
PtGA	Patient's Global Assessment of Disease Activity
PUVA	Psoralen and ultraviolet A
RCT	Randomized Control Trial
RCTC	Rheumatology Common Toxicity Criteria
REP	Residual Effect Period
SAE	Serious Adverse Event
SAP	Statistical Analysis Plan
s.c.	subcutaneous
SF-36	Short Form-36 Health Survey
SJC	Swollen Joint Count(s)
SPARCC	Spondyloarthritis Research Consortium of Canada
sPGA	Static Physician Global Assessment
SOC	System Organ Class
t _{1/2}	Half-life
SUSAR	Suspected Unexpected Serious Adverse Reaction
TB	Tuberculosis
TEAE	Treatment Emergent Adverse Events
TJC	Tender Joint Count(s)

TNF	Tumor necrosis factor
TNFi	Tumor necrosis factor inhibitor(s)
UV(A/B)	Ultraviolet (A/B)
VAS	Visual Analog Scale
W	Week
WBC	White Blood Count
WOCBP	Women of child-bearing potential

Pharmacokinetic and Statistical Abbreviations

AUC	Area under the plasma concentration-time curve
CL/F	Apparent clearance
C _{max}	Maximum observed plasma concentration
C _{trough}	Trough concentration
LOCF	Last observation carried forward
NRI	Non-responder imputation
OC	Observed cases
T _{max}	Time to maximum observed plasma concentration
V _{ss} /F	Volume of distribution

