**Table 8. Summary of Efficacy Variables and Corresponding Analyses**

Efficacy Variables	Summary Method
Categorical Efficacy Endpoints:	
Secondary Binary Endpoint: ACR20 responses at all measured time points	
 
• Point estimates and 95% CIs of the response rates
 
• Imputation: OC
 

Other Categorical Endpoints: At all measured time points:	
 
• Point estimates and 95% CIs of the response rates
 
• Imputation: OC
 

 
• ACR50
 
• ACR70
 
• Minimal disease activity (MDA)
 
• PASI75 response in subjects with a <math>\geq 3\%</math> baseline PsO BSA
 
• PASI90 response in subjects with a <math>\geq 3\%</math> baseline PsO BSA
 
• PASI100 response in subjects with a <math>\geq 3\%</math> baseline PsO BSA
 
• sPGA clear and almost clear in subjects with a <math>\geq 3</math> baseline PsO BSA
 
• Psoriatic Arthritis Response Criteria (PsARC)
 
• European League Against Rheumatism (EULAR) Response
 
• Presence of dactylitis (yes/no)
 
• No Progression of mTSS
 
	
Continuous Efficacy Endpoints	
Secondary Continuous Endpoint: Change from baseline in Study 1311.5 at Week 24 (Study 1311.5), Week 24 (Study M16-244) and Week 48:	
 
• Point estimates, 95% CIs of mean change from baseline together with SD, Min, Q1, Median, Q3 and Max
 
• Imputation: OC
 

Change from baseline in Study M16-244 at all measured timepoints:	
 
• mTSS
 
• HAQ-DI
 
• SF-36
 

**Table 8.****Summary of Efficacy Variables and Corresponding Analyses  
(Continued)**

Other Continuous Endpoints:	
At all measure time points as compared to baseline in Study M16-244:	

• Point estimates, 95% CIs of mean change from baseline together with SD, Min, Q1, Median, Q3 and Max

• For SF-36, spyderdiagram will be provided

• Imputation: OC

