### **Calculation Rules for ACR Criteria**

A subject will be classified as an ACR20 (ACR50, ACR70) responder, if the following conditions are met:

1.  $\geq 20\%$  ( $50\%$ ,  $70\%$ ) improvement from baseline in tender joint count (TJC)\* and
2.  $\geq 20\%$  ( $50\%$ ,  $70\%$ ) improvement from baseline in swollen joint count (SJC)\* and
3.  $\geq 20\%$  ( $50\%$ ,  $70\%$ ) improvement from baseline in at least 3 of the following 5:
  - Patient's assessment of pain
  - Patient's Global Assessment of Disease Activity for Arthritis (PtGA)
  - Physician's Global Assessment of Disease Activity for Arthritis (PhGA)
  - Patient's self-assessment of physical function (i.e., measured by Health Assessment Questionnaire (HAQ-DI score)
  - Acute-phase reactant value CRP

There are seven components to be evaluated to define an ACR response. Missing values for each component can occur due to missing assessment, a missed visit or due to dropout from the study. Depending on the pattern of the missing components, ACR responses may be or may not be determined using observed values only.

To maximize the utilization of observed information at certain visits and to be scientifically robust as possible, the principle to calculate ACR response is to minimize imputation whenever possible. "As Observed" ACR responses will be calculated

first based on a derived visit window instead of the nominal visit identifier collected from the CRF.

To calculate "as observed" ACR responses:

- Identify the observed component xx% improvement indicator (0/1/missing), 1 means achieving  $\geq$  xx% improvement from baseline and 0 means < xx% improvement from baseline (e.g., xx% representing 20%/50%/70%).
- ACRxx = 0 if TJC indicator = 0 OR SJC indicator = 0 OR at least 3 out of 5 components improvement indicators = 0;
- ACRxx = 1 if TJC indicator = 1 AND SJC indicator = 1 AND at least 3 out of 5 components improvement indicators = 1
- For all other cases, "as observed" ACRxx = missing since ACRxx cannot be determined.

The following table illustrates examples for as-observed ACR calculations.

Example	TJC 68	SJC 66	Component 1	Component 2	Component 3	Component 4	Component 5	ACR20- Response?
A	1	1	1	1	1	.	.	Yes
B	1	0	1	1	1	1	1	No
C	.	0	.	.	.	.	.	No
D	1	.	1	1	1	1	1	.
E	1	1	0	0	0	1	1	No
F	.	.	0	0	0	.	.	No
G	1	1	1	1	0	0	.	.

Legend: 1 =  $\geq$  20% improved compared to baseline; 0 = < 20% improved compared to baseline; " ." missing

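### Observed-case ACR and joint-count summaries at Week 48 describe a response-filtered subset and are expected, though not certain, to overstate response among all treated subjects

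*SAP*

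**What the plan says.** - **Missing data.** SAP 6.5 reports data as observed: "a subject who does not have an evaluation on a scheduled visit will be excluded from the summary for that visit". SAP Table 8 names observed cases (OC) as the handling for the categorical and continuous efficacy endpoints. SAP 10.3 adds: "The primary analysis for the above secondary efficacy endpoints will be performed based on the Safety Analysis Set with observed cases".
- **Mandatory removal.** Under Protocol 5.1, subjects who have not reached the ≥20% tender and swollen joint response "at 2 consecutive visits at Week 12 visit or thereafter, will be discontinued from the OLE study". Protocol 5.4.1 gives the same trigger, "at 2 consecutive visits at Week 12 visit, or thereafter".
- **What counts as failing.** SAP 5.1 describes the optional Week 4 dose as being "for subjects with < 20% improvement in tender joint count (TJC) or swollen joint count (SJC"), so failing either count is a failure.
- **Link to ACR.** SAP 10.7.1 states: "ACRxx = 0 if TJC indicator = 0 OR SJC indicator = 0". The rule applies at the 20, 50 and 70% levels.
- **After removal.** Protocol 5.4.1 provides an early end-of-treatment (EOT) visit, an end-of-study (EOS) visit and a phone call. Discontinued subjects are not replaced.
- **Population.** Protocol 8.1.1 and SAP 5.1 define the efficacy population as everyone dosed in this study.
- **Companion analyses.** None is specified for ACR or joint counts. The only sensitivity sentence in the SAP is optional and belongs to the mTSS section.

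**The concern.** Ordinary dropout may or may not be related to outcome. Here the protocol removes subjects because they fail a necessary component of ACR response, and the SAP then drops them from later denominators. The planned plot of response over time can rise with no patient improving. The exact confidence interval at Week 48 covers sampling error in the remaining subjects only. The subgroup summaries of the secondary endpoints in SAP 10.6 inherit the problem if removal differs between groups.

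A reader will see the denominator shrink but not why. SAP 8.0 lists adverse event, protocol violation, loss to follow-up, withdrawal by the subject and a residual category. Removal for protocol-defined non-response has no category of its own.

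**Working it through.** The plan states no response rate, removal rate or power to reproduce. Its figure of up to 180 subjects is an enrolment ceiling.

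**1. Removed subjects are ACR non-responders at the triggering visits.** Whether failure means either count, both counts or their sum, at least one count has improved by less than 20%. SAP 10.7.1 then sets ACR20, 50 and 70 to zero.

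**2. Where their later data fall.** SAP Table 1 windows are Days 128–211 (Week 24), 212–295 (Week 36), 296–351 (Week 48) and 352–378 (Week 52). Protocol 5.4.1 puts EOS 16 weeks (112 days) after the last dose. The Appendix C column heading puts it 16 weeks after EOT or early EOT. No drug is given at early EOT.

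| Removed at | EOS by Protocol 5.4.1 | EOS by Appendix C |
|---|---|---|
| Week 24 | 85 + 112 = Day 197 (Week 24 window) | 169 + 112 = Day 281 (Week 36 window) |
| Week 36 | 169 + 112 = Day 281 (Week 36 window) | 253 + 112 = Day 365 (Week 52 window) |

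No nominal day falls in Days 296–351, so filtering is most complete at Week 48. How far Weeks 36 and 52 are filtered depends on which EOS timing applies. One exception is possible: on the Appendix C timing, an early EOT two weeks after a Week 24 decision, with both ±4-day windows used, reaches 169 + 4 + 14 + 112 + 4 = Day 303. That would return few subjects.

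**3. Direction.** Let f be the fraction removed and r the Week 48 response rate the removed subjects would have had. NRI is non-responder imputation.

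- All treated = (1 − f) × OC + f × r
- OC excess = f × (OC − r)
- NRI shortfall = f × r

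OC is too high only if r < OC. NRI is further from the all-treated rate than OC when r > OC/2.

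**4. Illustrative size (all inputs assumed).** One million subjects per scenario were simulated:

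- probit random-intercept joint response;
- core-set subject effect correlated 0.7 with the joint effect;
- ACR20 held at 60% at every visit;
- the rule fully enforced, with both failures at Week 12 or later;
- removed subjects' course otherwise unchanged.

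| Joint response | Within-subject correlation | Removed | OC excess (points) | NRI shortfall (points) | Removed who would respond |
|---|---|---|---|---|---|
| 80% | 0.3 | 10.4% | 2.9 | 3.7 | 35% |
| 80% | 0.5 | 12.4% | 5.1 | 3.0 | 24% |
| 80% | 0.7 | 14.6% | 7.7 | 2.1 | 15% |
| 70% | 0.3 | 19.0% | 5.0 | 7.3 | 39% |
| 70% | 0.5 | 21.3% | 8.7 | 5.9 | 28% |
| 70% | 0.7 | 23.7% | 12.9 | 4.4 | 19% |

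Check of the first row, with OC = 62.9% and r = 35.4%: 0.104 × (62.9 − 35.4) = 2.9 and 0.104 × 35.4 = 3.7. Here r exceeds 62.9/2 = 31.5, so NRI misses by more than OC.

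Milder cases give less:

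- At 90% joint response, with correlation 0.1 to 0.7, 2.4 to 6.3% are removed and the excess is about 0.3 to 3.3 points.
- At correlation 0.1 with 70–80% joint response, the excess is about 0.8 to 1.6 points, while NRI is roughly 4 to 9 points too low.
- With no within-subject persistence r equals OC, and the excess is zero.

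If a failure at Weeks 4 and 12 also triggers removal, the excess over correlations 0.3 to 0.7 becomes 3.9–9.5 points (80% joint response) or 6.8–15.6 points (70%).

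**5. Extreme case.** Take 180 subjects and 108 responders, with no removed subject able to respond. All treated is 108/180 = 60.0% (exact 95% CI 52.4–67.2). With 10% removed, OC is 108/162 = 66.7% (58.8–73.9). With 20% removed, it is 108/144 = 75.0% (67.1–81.8).

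**The case against.** The strongest reply is that observed cases are a legitimate descriptive choice in a single-arm extension. Safety is the primary objective, there is no primary efficacy endpoint, and nothing is tested. That stands, and is why OC should be kept.

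The size is also open. Favourable assumptions bring the excess under one point, against an exact interval of about ±7 points at 180 subjects. SAP 7.4 plans to count subjects who met withdrawal criteria but stayed in; incomplete enforcement would shrink the effect. Both points stand. They limit the magnitude, not the mechanism.

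Some of the problem is already visible. Counts with percentages, n for continuous endpoints and discontinuation by reason are planned, and the recorded reason might identify non-response. We do not have the eCRF, so that cannot be settled here.

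Several stronger readings are tempting but unsupported:

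- **That OC certainly overstates response.** Removed subjects' Week 48 status is unobserved, and some could have responded by then.
- **That NRI gives the correct rate.** It can miss by more than OC, and it also scores withdrawals for adverse events or by choice as failures.
- **That an NRI analysis was planned and dropped.** "Non-responder imputation" appears in the protocol's abbreviation list beside LOCF and OC, and the protocol's statistical text uses none of the three.
- **That a joint-count bias can be quoted.** Simulations of percent improvement do not measure the planned endpoint, which is absolute change in count.
- **That skin, dactylitis or mTSS results are inflated too.** Direction and size are unknown for these.

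**Conclusion.** The point holds for ACR20/50/70 and for TJC and SJC. Followed as written, the plan produces a Week 48 summary of a response-filtered subset, with no companion analysis for everyone treated. Overstatement is expected because subjects are removed for joint non-response, but it requires that they would have responded less often than those retained.

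The illustrative ACR20 excess at Week 48 runs from about 0.3 points (90% joint response, correlation 0.1) to about 13 points (70%, correlation 0.7). It is zero without persistence. These figures assume a true ACR20 of 60%, full enforcement and both failures at Week 12 or later; none of the rates comes from the documents. For joint counts the expected direction is the same and no magnitude is claimed.

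Confidence is high on the mechanism, not on the size. The harm is to how the durability curve is read; the safety objective is untouched.

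**What to change.** In SAP 6.5, 10.3 and Table 8:

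1. Keep OC as the main summary.
2. For ACR20/50/70 only, prespecify an NRI summary on the full Safety Analysis Set, counting subjects who discontinued study drug early as non-responders at later visits. Label it a conservative lower companion, not an unbiased estimate, and note that it can be further from full follow-up than OC when within-subject correlation is low.
3. Report n/N by visit for both.
4. Do not extend NRI to skin, dactylitis or mTSS endpoints. A skin responder removed for joint non-response would be scored a failure, and presence of dactylitis has no defined responder.
5. Optionally add a repeated-measures mixed model for change in TJC and SJC as a sensitivity analysis, without claiming that it removes the bias.

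In SAP 8.0, add protocol-defined non-response to the discontinuation reasons.

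Separately, the EOS timings in Protocol 5.4.1 and Appendix C must be reconciled, because they decide which visit window discontinued subjects' EOS data enter. No clinical rule is proposed.

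The cost is SAP wording and a few tables. NRI needs no new data; the new disposition category needs none if the recorded reason identifies non-response. The downside is less favourable ACR rates at later visits that may understate response: by about 2 to 7 points in the tabulated scenarios, and more at low correlation.
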